## Study Protocol

Alcohol is a highly addictive substance and alcohol dependence is a chronically relapsing disorder. It induces tolerance such that increased doses of the alcohol are required to achieve the desired effects and is associated with adverse symptoms during its acute withdrawal. Progressing disease is accompanied with neglect of alternative interests, and social, family and occupational activities. Attempts to quit are often unsuccessful and the patient continues to use the substance despite knowledge of physical and/or psychological harm caused by alcohol (1). Alcohol dependence is thus a debilitating disorder that harms not only the individual, but inflicts significant costs to society, including loss of productivity, security challenges, crime and lawlessness, increasing health care costs and a myriad of negative social consequences (2).

Craving is a common manifestation in all drug addictions. It is defined as the “pressing, urgent and irrepressible desire to give in to the substance” (3), resulting in an uncontrolled urge to consume a drug, with strong obsessions about and irresistible compulsions to use (4), even when the individual is well aware of the consequences that its use can bring to his life. Craving is now considered as part of the diagnosis criteria for Substance Use Disorders under the A4 criteria in the DSM-5 (1, 5, 6). One reason to add craving to the diagnostic criteria was that that it activates brain regions related to the reward system (7, 8). Indeed, craving can be caused by an alteration of the relevant brain circuitry, that may persist even when the individual is not currently using the substance, but is exposed to stimuli that are associated with it (1, 9, 10), constituting a recognized central driving force for successive relapses and perpetuation of drug use (11, 12).

Psychosocial and pharmacological approaches, although essential, have shown limitations and modest efficacy in the treatment of alcohol dependence (13). Therefore, the development of more effective treatments or alternatives improving the efficacy of the current approaches is highly desired.

Transcranial direct current stimulation (tDCS) is a non-invasive brain stimulation technique in which a weak current is applied to the brain for several minutes through electrodes, resulting in a polarity-dependent modulation of brain activity (14, 15). Considering that a single bilateral tDCS, either left cathodal/right anodal or left

anodal/right cathodal, over the dorsolateral prefrontal cortex (dlPFC) showed to reduce alcohol craving in AUD patients (16), but the repetitive unilateral anodal tDCS over the left dlPFC increased instance of relapses in AUD patients (17), in the following study in AUD outpatients, we applied five consecutive sessions of bilateral tDCS, having the cathodal electrode over the left and the anodal over the right dlPFC, and showed a reduced probability of relapse to the use of alcohol (18). Half (50%) of the AUD patients treated with tDCS, as compared to only 11.8% of subjects from the sham-tDCS group, were completely abstinent at the end of six months following the intervention. However, in this study craving during the period of brain stimulation was not significantly changed (18).

The extension of tDCS sessions may clinically matters as 10 daily sessions have shown to result in more effective and long-lasting effects than 5 daily sessions (19, 20). Therefore, in the present study we aimed to investigate whether an intensified intervention with ten sessions of tDCS bilaterally applied over the dlPFC would reduce craving for alcohol use in AUD inpatients.

## **Material and Methods**

We report this clinical trial according to CONSORT guidelines. This trial was registered under Clinical Trials.gov number NCT02091284.

### *Participants*

AUD patients of both genders were successively recruited between June of 2015 and January of 2018 from three specialized clinics for drug dependence treatment, one public and two privates, from the State of Espírito Santo, Brazil. These specialized services applied standard protocols for the treatment of drug addiction, consisting of psychosocial approaches –conducted by a professional team of psychologists, nurses, social workers and physicians, and pharmacotherapy, including benzodiazepines, vitamin B, disulfiram and, when necessary, antidepressants, anxiolytics, antihypertensive, and gastric medications, and folic acid. Two dropouts occurred after randomization. One dropout had to be hospitalized due to clinical instability and another missed many stimulation sessions.

The inclusion criteria for this study were: (1) male and female patients over the age of 18 years; (2) met criteria for alcohol dependence according to the Classification of Mental and Behavioral Disorders (ICD-10) and the Diagnostic and Statistical Manual of Mental Disorders, fifth edition (DSM-5), as determined by clinical evaluation; (3) in stable clinical condition with no need for emergency care; (4) able to read, write, and speak Portuguese; and (5) without severe withdrawal signs or symptoms at baseline.

Exclusion criteria included: (1) a condition of intoxication or withdrawal due to a substance other than alcohol, (2) unstable mental or medical disorder or substance abuse or addiction other than alcohol dependence, except nicotine and/or caffeine or history of marijuana use during adolescence; (3) diagnosis of epilepsy, convulsions, or delirium tremens during the abstinence of alcohol; (4) a previous history of drug hypersensitivity or adverse reactions to diazepam or other benzodiazepines and haloperidol; (5) any contraindication for electrical brain stimulation procedures such as electronic or metal implants.

Ethical approval was provided by the Brazilian Institutional Review Board of the Federal University of Esprito Santo (CAAE 19403713.6.0000.5060), Brazil, and it was registered in clinicaltrials.gov (<https://clinicaltrials.gov/ct2/show/NCT02091284>). The study was conducted in strict adherence to the Declaration of Helsinki and is in accordance with the ethical standards of the Committee on Human Experimentation of the Federal University of Esprito Santo, ES, Brazil, where this study was conducted. Subjects were fully informed about the experimental protocol and voluntarily signed an informed consent form before the start of the study.

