#### *3-months follow-up: Alcohol use relapses*

After their discharge from the hospital, patients from sham- and real tDCS groups were followed-up for three months, corresponding to a period of initial remission according to DSM-5, regarding alcohol use relapses. Alcohol use relapse here was considered as the first episode of return to the previous uncontrolled pattern of alcohol use (drinks per day) (18). Information of these relapses were gathered directly

when patients regularly returned to the hospital for clinical follow-up after their discharge and/or by self-report or reports of family members by telephone calls.

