## Statistical Analysis

We powered the study for a small effect size given our hypothesis that tDCS would be associated with a relevant reduction in craving scores. Thus, assuming a small effect size of 0.3 specified for SPSS in G\*Power 3.1 for a repeated measure (5 measures) within-between interaction analysis of variance (ANOVA) as principal statistical test for the craving analysis with a power of 80%, a two-sided probability of a type I error of 5%, a minimum of 38 subjects would be necessary; however to account for waiving or dropouts expected to be very common in this condition, we increased the estimated sample to approximately 20%, resulting in 45 to 46 subjects (22 to 23 subjects in each group).

Age, patterns of alcohol use and 5-items OCDS were normally distributed according to D'Agostino & Pearson normality test, thus they were analyzed by parametric tests.

Besides the two-way ANOVA (sham-tDCS and tDCS groups as between-subjects factor) with repeated measures (five time-points as within-subjects factor) followed by Bonferroni's multiple comparisons as *post-hoc* test, linear regression analyses were done over craving scores obtained over the respective five time-points for both groups and the slopes of the respective curves were compared using a modified version of the *t* test according to Zar (1984), which is equivalent to analysis of covariance. Additional comparisons between initial and final OCDS scores were done by paired *t* tests for each group, and differences between final and initial scores were compared between sham-tDCS and tDCS groups with unpaired *t* tests. Effect sizes were calculated using Cohen's *d* and corrected by Hedges's  $g_s$  for unpaired and Hedges'  $g_{av}$  for paired *t*-tests (Lakens, 2013).

Age and patterns of alcohol use were compared between groups by unpaired *t*-test. For all other non-parametric data, Chi-square or Fisher tests were used to compare results between sham and real tDCS groups.

A two-tailed p-value of 0.05 or less was considered to indicate statistical significance. SPSS Statistics Base 24.0 (SPSS Inc, USA) and GraphPad Prism 7.0

(GraphPad Software Inc, USA) were employed for statistical analysis and graphic presentations.

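### The principal craving ANOVA has no analysis set or missing-data rule, so patients classed as dropouts after randomisation, one for missing stimulation sessions, probably fall out of the randomised comparison

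*Combined protocol and SAP*

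**What the plan says.** **Participants** reports: "Two dropouts occurred after randomization. One dropout had to be hospitalized due to clinical instability and another missed many stimulation sessions". It gives neither the arm of each patient nor the number of missed sessions that makes a dropout.

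**Statistical Analysis** names a "repeated measure (5 measures) within-between interaction analysis of variance (ANOVA) as principal statistical test for the craving analysis". It adds Bonferroni comparisons, a between-group comparison of regression slopes over the five time points, paired t tests of first against last score within each group, and an unpaired t test of the change between groups. The minimum of 38 patients is raised by about 20% to 45-46, "to account for waiving or dropouts expected to be very common in this condition".

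**Craving assessment** and **Procedures** both give five OCDS measurements: one before treatment, three during it and one after.

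**3-months follow-up** says: "After their discharge from the hospital, patients from sham- and real tDCS groups were followed-up for three months". It gives no denominator.

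No section defines an analysis set, says patients are analysed as randomised, says whether craving was still scored once sessions stopped, or names a method for missing scores. Material and Methods says that the trial is reported according to CONSORT, but no such rule follows.

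**The concern.** Missing sessions is non-adherence to the intervention. It does not in itself mean that outcome data are missing. Once such a patient is called a dropout and the principal test accepts only complete sets of five scores, stopping treatment can become removal from the analysis. Both reported events came after randomisation, and both could depend on the assigned stimulation or on how the patient was doing.

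A complete-case ANOVA then estimates the effect in patients who stayed and attended, not the difference between the groups as randomised. If the patients who leave are those whose craving is not falling, the group-by-time effect is biased. It shrinks if they leave the sham arm and grows if they leave the active arm. Because many has no definition, the analysed set also depends on a judgement made after randomisation.

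**Working it through.** **1. The plan's own figure.** Inputs from Statistical Analysis: f = 0.3 with the SPSS effect-size option in G\*Power, k = 2 groups, m = 5 measures, alpha 0.05, power 80%. Sphericity (epsilon = 1) is assumed because the document gives no value.
- Noncentrality: lambda = f² × (N − k) × (m − 1).
- Degrees of freedom: (k − 1)(m − 1) = 4 and (N − k)(m − 1).
- N = 38: lambda = 0.09 × 36 × 4 = 12.96, power 82.2%. N = 36 gives 79.6%, so 38 is the smallest even total and the stated figure is reproduced.
- Allowance: 38 × 1.20 = 45.6, which matches 45-46. This step treats dropouts as patients who do not count towards the 38.

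**2. Power after two losses.** Two of 45-46 is 4.4% to 4.3%.

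| Total N | Power |
|---|---|
| 45 to 46 (all planned) | 89.2% to 90.0% |
| 43 to 44 (two removed) | 87.5% to 88.4% |

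The loss is under 2 percentage points, so power is not the issue.

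**3. Shift in one arm's mean.** Suppose each omitted patient's craving change would have been D standard deviations worse than that of the rest of the arm (D is assumed). The shift is (number omitted) × D / n, with n = 22 to 23 per arm.
- One omitted, D = 1: 1/23 to 1/22 = 0.043 to 0.045 SD.
- Two omitted from the same arm, D = 1: 2/23 to 2/22 = 0.087 to 0.091 SD.
- Two omitted from the same arm, D = 2: 4/23 to 4/22 = 0.174 to 0.182 SD.

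**4. Illustrative simulation.** All inputs are assumed: 23 per arm, SD 4 at each time point, correlation 0.6 between any two scores, and linear falls of 4 points (sham) and 7 points (active), so the true difference in change is -3.0. A non-responder is a patient with no fall by the third score. The standard error of the difference in change is √(2 × 16 × (1 − 0.6) × 2/23) = 1.05.

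| Loss pattern | Complete-case estimate |
|---|---|
| None | about -3.0 |
| Two sham non-responders | about -2.8 |
| One non-responder per arm | about -3.0 |
| 60% of sham non-responders (about 4 patients) | about -2.55 |

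Two sham losses shift the estimate by about 0.2 points, or 0.2/1.05 ≈ 0.2 standard errors. When 60% of non-responders leave the active arm instead (sham fall varied from 2 to 4 points, 2.3 to 3.4 losses), the complete-case estimate is exaggerated to between -3.28 and -3.38. In the 60% scenarios, a likelihood-type analysis using every available score stays near -3.0 in either direction.

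**The case against.** The strongest reply is that no sentence says either patient was excluded, lacked an OCDS score or stopped being assessed. Craving was scored weekly, on a timetable separate from the sessions, so missed sessions need not mean missed scores. This stands: exclusion is an inference from the dropout label, the complete-data requirement of the named test and the way the sample was inflated.

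The need for all five scores also applies only to the ANOVA. The first-against-last t tests need two scores, and the slope comparison does not inherently need all five. That stands too, but neither is the principal test.

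Three stronger readings are tempting, and the documents do not support them.
- *The two patients were left out of the relapse count.* Follow-up starts at discharge and carries no requirement to complete stimulation. The document does not say whether these two were followed.
- *The trial loses its power.* Even at N = 37, one below the stated minimum, power is 80.9% under the plan's effect size with sphericity.
- *The bias is large.* The shift to about -2.55 needs about four losses, all from one arm and all non-responders. Two are reported, in unknown arms. Common dropout was a planning expectation.

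Finally, stating the analysis set, the missing-data handling and the dropouts' arms would close the gap in wording. It would not be enough if the principal test remained an ANOVA that cannot use a partial set of scores.

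**Conclusion.** The concern holds with moderate confidence. Followed as written, the principal craving test deletes any randomised patient lacking one of five scores, and nothing in the document keeps non-adherent patients in. That both reported dropouts are left out is a fair inference, not a stated fact.

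What is at stake is bias and the population described. The direction cannot be determined without the arms. The size is probably modest: from almost no shift (one loss per arm) to about 0.2 points on a true difference of -3.0 (two sham non-responders), under the assumed SD, correlation and trajectories. It would grow if dropout were as common as the plan expected. The power figures rest on f = 0.3 and sphericity.

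**What to change.** - **Principal craving test:** a linear mixed model for repeated measures with group, categorical time, group-by-time and a within-patient covariance structure. Fit it to every randomised patient with at least one OCDS score, in the assigned arm, whatever number of sessions was received. State the missing-at-random assumption.
- **ANOVA:** keep it as a supplementary analysis labelled as completers only.
- **Dropouts:** state the arm of each, which OCDS scores each has, whether scoring continued after sessions stopped, and what counted as missing many sessions.
- **Relapse:** make the denominator all randomised patients by arm, with a sensitivity analysis counting unknown status as relapse. State whether the two dropouts were followed.
- **Timing:** recruitment is reported as finished, so date the change and show both craving analyses.

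The cost is revised SAP wording and one further model run, with no new patients or visits. The document names SPSS Statistics Base 24.0, so check that this edition fits mixed models; the remedy does not depend on one package. There is a small downside: including patients with few sessions may slightly dilute the effect. The required N of 38 is not altered by the choice of analysis set.

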#### *Direct Current (DC) stimulation*

The intervention in this clinical trial was transcranial DC stimulation (tDCS). In each session, tDCS was applied via two carbonated silicone electrodes (35 cm^2) with a thick layer of high-conductive EEG paste on the contact surface connected to a DC-Stimulator (DC-Stimulator Plus, NeuroConn, Ilmenau, Germany) for 20 minutes with fade-in and fade-out periods of 30 seconds each. Intensity was set to 2 mA.

The cathode was placed above F3 (according to the EEG international 10 –20 system), corresponding to the left dlPFC, and the anode was positioned above the right

dIPFC (F4). For the sham stimulation procedure, the stimulator automatically switched off after 30 seconds of either anodal or cathodal stimulation yielding sensations typically elicited by tDCS. Sham- or real tDCS was applied once a day, every other day, including weekends, until completion of 10 sessions (Fig. 1).

#### *Craving assessment: 5-items OCDS*

Craving was scored with a brief scale composed of 5 items (1, 2, 4, 5, and 13) from the Obsessive-Compulsive Drinking Scale (OCDS) (21-23), which assesses craving in a narrow sense according to De Wildt et al. (24).

Questions of this brief scale allow quantification of thoughts and feelings (obsessions), and behavioral intentions (24), and are answered on a scale ranging from 0 to 4, resulting in a total score between 0 and 20. They ask how much of a person's time (total per day), when the drug is not used, is occupied by thoughts, ideas, desires, or impulses related to alcohol and its effects; how frequently these thoughts, ideas, desires, or impulses related to alcohol and its effects occur; how much distress or disturbance these ideas, thoughts, impulses or desire related to alcohol use cause when the person is under withdrawal; how much effort the person has to make to resist these thoughts, ideas, desires, or impulses, or how much energy he/she has to spend to think of something else when they enter the mind under withdrawal; and finally ask about the person's drive to use alcohol.

This scale was applied in the week before the beginning of the real or sham-tDCS treatment (1st measurement), during the treatment over approximately 3-weeks (2nd, 3rd and 4th measurements) and in the week after the end of the brain stimulation protocol (5th measurement).

#### *3-months follow-up: Alcohol use relapses*

After their discharge from the hospital, patients from sham- and real tDCS groups were followed-up for three months, corresponding to a period of initial remission according to DSM-5, regarding alcohol use relapses. Alcohol use relapse here was considered as the first episode of return to the previous uncontrolled pattern of alcohol use (drinks per day) (18). Information of these relapses were gathered directly

when patients regularly returned to the hospital for clinical follow-up after their discharge and/or by self-report or reports of family members by telephone calls.

### *Procedures*

Those patients who were eligible for study participation according to the inclusion and exclusion criteria described above and agreed to participate in this study signed an informed consent form (Fig. 1). All data were originally acquired from participants participating in a randomized sham-controlled double-blind clinical trial to investigate the efficacy of tDCS treatment of alcohol dependence.

After global physical and clinical examination, subjects were randomly assigned to one of the two intervention groups (sham- and real tDCS) in a 1:1 ratio using a computer-generated block randomization sequence that was kept with the unblinded study coordinator (not involved in recruitment) and only revealed to the co-investigator conducting treatments immediately before the first session.

Craving (5-items OCDS) was measured before and after completion of the treatment and once per week during the three-weeks treatment, resulting in five measurements (Fig. 1). Alcohol use relapses after hospital discharge were verbally obtained from patients, families or caregivers.

Participants and experimenters were blinded for brain stimulation assignments from the beginning of the study protocol up to the end of the 3-months follow-up after the end of sham-tDCS or real tDCS treatment, configuring a double-blind experimental design.

## Statistical Analysis

We powered the study for a small effect size given our hypothesis that tDCS would be associated with a relevant reduction in craving scores. Thus, assuming a small effect size of 0.3 specified for SPSS in G\*Power 3.1 for a repeated measure (5 measures) within-between interaction analysis of variance (ANOVA) as principal statistical test for the craving analysis with a power of 80%, a two-sided probability of a type I error of 5%, a minimum of 38 subjects would be necessary; however to account for waiving or dropouts expected to be very common in this condition, we increased the estimated sample to approximately 20%, resulting in 45 to 46 subjects (22 to 23 subjects in each group).

Age, patterns of alcohol use and 5-items OCDS were normally distributed according to D'Agostino & Pearson normality test, thus they were analyzed by parametric tests.

Besides the two-way ANOVA (sham-tDCS and tDCS groups as between-subjects factor) with repeated measures (five time-points as within-subjects factor) followed by Bonferroni's multiple comparisons as *post-hoc* test, linear regression analyses were done over craving scores obtained over the respective five time-points for both groups and the slopes of the respective curves were compared using a modified version of the *t* test according to Zar (1984), which is equivalent to analysis of covariance. Additional comparisons between initial and final OCDS scores were done by paired *t* tests for each group, and differences between final and initial scores were compared between sham-tDCS and tDCS groups with unpaired *t* tests. Effect sizes were calculated using Cohen's *d* and corrected by Hedges's  $g_s$  for unpaired and Hedges'  $g_{av}$  for paired *t*-tests (Lakens, 2013).

Age and patterns of alcohol use were compared between groups by unpaired *t*-test. For all other non-parametric data, Chi-square or Fisher tests were used to compare results between sham and real tDCS groups.

A two-tailed p-value of 0.05 or less was considered to indicate statistical significance. SPSS Statistics Base 24.0 (SPSS Inc, USA) and GraphPad Prism 7.0

(GraphPad Software Inc, USA) were employed for statistical analysis and graphic presentations.

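### The power statement calls its target effect small, but the 38 subjects rest on f = 0.30 on the scale the plan names, and the trial is not powered for materially smaller interactions on that scale

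*Combined protocol and SAP*

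**What the plan says.** All of the relevant text is in the Statistical Analysis section of the combined protocol and SAP.

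- The aim of the calculation: "We powered the study for a small effect size given our hypothesis that tDCS would be associated with a relevant reduction in craving scores".
- The numerical input, again with the label: "assuming a small effect size of 0.3 specified for SPSS in" G*Power 3.1.
- The test: "for a repeated measure (5 measures) within-between interaction analysis of variance (ANOVA) as principal statistical test for the craving analysis", with 80% power and a 5% two-sided type I error.
- The result: "a minimum of 38 subjects would be necessary". About 20% is then added for dropout, "resulting in 45 to 46 subjects (22 to 23 subjects in each group".
- The decision rule: "A two-tailed p-value of 0.05 or less was considered to indicate statistical significance".
- A further comparison of craving: "differences between final and initial scores were compared between sham-tDCS and tDCS groups with unpaired" *t* tests, with Hedges-corrected effect sizes. No confidence interval is mentioned.

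The section gives no benchmark for *small*. It also gives no target difference in OCDS points, no standard deviation, no correlation between the repeated measures and no sphericity value.

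**The concern.** An effect size of 0.3 has no meaning until its scale is known. The plan names the SPSS option, in which f is tied to partial eta-squared and already absorbs the within-patient correlation. On that scale 0.30 lies above the value usually called medium (0.25) and well above the value usually called small (0.10). The label therefore claims a sensitivity that the calculation beside it does not deliver.

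What is at stake is how the result is read. The trial judges craving by p at 0.05 and plans point effect sizes without intervals. A reader who relies on the label could count a non-significant interaction as stronger evidence against a modest craving benefit than this design can supply.

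**Working it through.** **Inputs.** From Statistical Analysis: f = 0.30, SPSS option, m = 5 measures, alpha 0.05, power 80%, N = 38 rising to 45 to 46. From Procedures: k = 2 groups, 1:1. Assumed because the documents are silent: epsilon = 1 (sphericity) unless stated, and 0.10 and 0.25 as the conventional small and medium f.

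**Formula (SPSS option, group-by-time interaction).** lambda = f² × (N − k) × (m − 1) × epsilon; df1 = (k − 1)(m − 1) × epsilon; df2 = (N − k)(m − 1) × epsilon. Power is the noncentral F probability above the 5% critical value.

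**1. The plan's own figure.** At N = 38: lambda = 0.09 × 36 × 4 = 12.96, df 4 and 144, power 82.2%. At N = 36: lambda = 0.09 × 34 × 4 = 12.24, df 4 and 136, power 79.6%. The smallest balanced total is 38, as stated. The inflation also agrees: 38 × 1.2 = 45.6.

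**2. Is 0.3 really on the SPSS scale?** On the raw-SD scale, lambda = f² × N × m / (1 − rho). There f = 0.30 would need 28, 20, 16 or 10 patients in equal groups at rho 0, 0.3, 0.5 or 0.7. Cohen's option gives 36. Only the option the plan names gives 38.

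**3. Partial eta-squared.** This is f²/(1 + f²): 0.09/1.09 = 0.083 at f = 0.30; 0.0625/1.0625 = 0.059 at 0.25; 0.01/1.01 = 0.010 at 0.10.

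**4. Sensitivity without any benchmark.** The smallest f with 80% power is 0.293 at 38 patients, 0.267 at 45 and 0.264 at 46.

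**5. Power at smaller f (SPSS scale, epsilon = 1).**

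| f | N = 38 | N = 46 |
|---|---|---|
| 0.10 | 13.0% | 15.2% |
| 0.15 | 25.4% | 30.9% |
| 0.20 | 43.9% | 53.0% |
| 0.25 | 64.7% | 74.9% |
| 0.30 | 82.2% | 90.0% |

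For f = 0.10 without sphericity: 11.9% (38) and 13.6% (46) at epsilon 0.75; 10.6% (38) and 12.0% (46) at epsilon 0.5.

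**6. The same effect in SDs of change.** Assume compound symmetry and a group difference that grows linearly from 0 to D over the five measurements. The deviations from its mean are D × (−0.5, −0.25, 0, 0.25, 0.5), with sum of squares 0.625 D². Then lambda = (N/4) × 0.625 D² / [sigma²(1 − rho)]. The SD of change is sigma × √(2(1 − rho)). Writing d for D divided by that SD, lambda = 0.3125 × N × d², and rho cancels. At N = 38, d² = 12.96/(0.3125 × 38) = 1.091, so d = 1.04. In SDs of a single score, D = 1.04 × √(2(1 − rho)), which is 1.04 at rho 0.5, 0.66 at 0.8 and 0.47 at 0.9.

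**7. The raw-SD scale.** SPSS f = 0.30 at N = 38 corresponds to raw f = √(12.96 × (1 − rho)/190): 0.26, 0.18, 0.12 and 0.08 at rho 0, 0.5, 0.8 and 0.9. Power for raw f = 0.10 at 38 and 46 patients is 16% and 19% at rho 0, 30% and 36% at 0.5, 67% and 77% at 0.8, and 95% and 98% at 0.9. It reaches 80% only at rho of about 0.85 (38) or 0.81 (46).

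**8. Is 0.30 an exclusion bound?** Take N = 38 and p = 0.051, so F is about 2.42 on 4 and 144 df. Inverting the noncentral F for the upper limit of a two-sided 95% interval gives lambda of about 22.2, so f = √(22.2/144) = 0.39.

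**The case against.** The best defence is that *small* is never defined, so no figure in the plan contradicts it. The 0.10 benchmark is a convention from outside the documents. Because the SPSS-scale f absorbs the correlation between measures, that benchmark does not carry over cleanly. At a within-patient correlation near 0.85, f = 0.30 on the SPSS scale is about 0.10 on the raw-SD scale, and the label would then look about right. The plan also prints the value, scale, software, test and N next to the adjective, so a careful reader can recover the true sensitivity. Nothing in the text says that a non-significant interaction will be read as absence of effect.

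Much of this stands. The 13% to 15% applies only to f = 0.10 on the named scale under sphericity, and it rests on an assumed benchmark. Nothing was miscalculated.

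The high-correlation argument does not rescue the label, however. The plan states no correlation. In SDs of change the target is about 1.04 whatever the correlation (linear profile, compound symmetry). Even at a correlation of 0.9 it is about 0.47 SDs of a single score. The conclusion also does not depend on choosing 0.10, since at 38 patients power is below 80% for every f under 0.293 on the plan's scale.

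**Conclusion.** Wrong as written, and minor: the sensitivity is mislabelled, but there is no arithmetic error. The 38 is right for f = 0.30 on the SPSS scale with sphericity assumed. The trial reaches 80% power down to f = 0.293 at 38 patients and 0.264 at 46, and not for materially smaller interactions. If small means f = 0.10, power is about 13% to 15% under sphericity and 10.6% to 13.6% at epsilon 0.5 to 0.75. The 1.04 SDs of change assumes a linear profile and compound symmetry.

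Two stronger readings are not supported. A reader might infer that the sample size is wrong, or that the trial has 13% to 15% power for a small effect on any scale. The first fails because 38 reproduces. The second fails because power on the raw-SD scale depends on a correlation the documents do not give. A reader might also infer that a non-significant interaction rules out f of 0.30 or more. It need not: with 38 patients and p = 0.051 the upper 95% limit for f is 0.39.

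**What to change.** Delete *small* in both places and replace the statement with wording such as:

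> A total of 38 subjects gives at least 80% power for a group-by-time interaction of f = 0.30 (SPSS parameterisation, partial eta-squared 0.083), assuming sphericity; the study is not powered for materially smaller interactions on this scale.

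Report the 95% confidence interval for the between-group difference in change beside the planned Hedges' g, and base any statement about which effects are excluded on that interval. Do not add a sentence saying that a non-significant interaction fails to exclude effects below f = 0.30. It would invite the reading that larger effects are excluded.

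The cost is one reworded paragraph and one interval from data already planned, with no added patients. The only drawback is a less favourable description of the trial's sensitivity.
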